Cover page

Trial Title:

**A New Conception About Individualized Treatment
Allocation for HCC—Using Machine Learning**

**Unit of Study: The Second Affiliated Hospital of Air
Force Military Medical University**

Principal Investigator: [name]

Date: 2023-8-20

NCT number and document date have not been assigned

Study protocols

1. Study population

Between January 2010 and October 2021, a total of 5816 consecutive HCC patients receiving LR or TACE from 15 Chinese tertiary hospitals were retrospectively screened. HCC was diagnosed based on either imaging or pathological results as previously described [1]. To better fit LR and TACE therapies into AI models, liver-confined HCC was incorporated with LR or TACE candidates according to the latest criteria of the BCLC guidelines [2]. Patients with well-preserved liver function, good PS (Eastern Cooperative Oncology Group [ECOG] PS0), and no vascular invasion or extrahepatic spread were divided into BCLC 0, A, and B stages, where they could undergo LR and TACE therapy. In addition, mild tumor-related symptoms (PS1) have not been an absolute contraindication for LR as per recent research [3], and the guidelines of the American Association for the Study of Liver Diseases (AASLD) expanded the PS 0–1 in the BCLC 0–B stage, considering the conceptual overlap between them [4, 5]. Here, the inclusion criteria were as follows: (a) diagnosed with HCC; (b) receiving LR or TACE therapy; (c) complete clinical information; (d) preserved liver function (Child-Pugh Score [CPS] ≤ 7); and (e) PS 0–1. The exclusion criteria included: (a) vascular invasion or extrahepatic spread; (b) decompensated liver cirrhosis (gastrointestinal bleeding, ascites, or hepatic encephalopathy); (c) younger than 18 years; and (d) duration of follow-up of fewer than 30 days. Image assessment, including the diameter of the largest nodule (tumor size, measured in centimeters) and tumor number, was performed by two independent investigators via CT or MRI. The flow chart of the study is depicted in Figure 1. Eligible patients were randomly stratified into train and validation cohorts (ratio=0.85: 0.15). The study was approved by the committee on human research of participating centers and approved by the Medical Ethics Committee of the Tangdu hospital (TDLL-202302-06) and Daping Hospital of the Army Medical University (2022(186)). Written informed consent to participate in this study was provided by the participants' legal guardian/next of kin.

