2. Treatment procedures

During the LR procedure, patients were placed in the supine position, often under general anesthesia of the trachea. Operators fully exposed the surgical field and explored the location of the tumor and vascular anatomy. After blocking the first liver portal, operators ligated the liver section blood vessels and bile ducts, assessed the distance between lesions, and ensured residual liver volume. Multiple tumors were removed by en bloc resection or multiple LR with good liver function, including indocyanine green (ICG) clearance tests ^[6].

During the TACE procedure, an emulsion of mixtures of lipiodol (3–30 ml) and chemotherapeutic drugs was injected, including doxorubicin (10–50 mg), cisplatin (10–110 mg), epirubicin (10–50 mg), or oxaliplatin (100–200 mg). Afterward, either a gelatin sponge or polyvinyl alcohol foam (PVA) particles were introduced to embolize tumor-feeding vessels either selectively or super-selectively ^[7].

3. Model development

According to survival algorithms in the existing literature, 10 kinds of available AI models were developed in the training set. The details of data preprocessing and model development are shown in Supplement 1. To reduce the overfitting of survival models, the AI algorithms in the training cohort were developed by adopting K-fold cross-validation. In each fold, hyperparameter optimization was tuned by an exhaustive cross-validation grid search, and the models were refitted in the training set with the optimal score parameters. The selection criterion of the AI models was defined as a C-index ≥ 0.7 . Based on the AI models, the predictive performance (censored C-index and mean cumulative/dynamic area under the receiver operating characteristic curve [auROC]), calibration curves, and Brier score (BS) were evaluated. The BS represents the mean square difference between observed patient status and predicted survival probabilities; it ranges from 0 to 1 and is negatively correlated with the discrimination and calibration of algorithms. IBS is defined as an overall estimation of BS; a value lower than 0.25 is deemed applicable in the clinic ^[8].

4. Model estimation

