An ensemble model was developed and named the precise treatment allocation (PTA) model in our study. It could accurately predict the survival probability of each patient by alternating the different treatments. The inputs of the PTA model mainly comprise four modules: (a) liver function, such as serum albumin, serum bilirubin, and coagulative function indexes; (b) tumor burden, including serum alpha-fetoprotein (AFP), tumor size, and tumor number; (c) demographic data, such as age and gender; and (d) routine laboratory indications, such as routine blood examination and kidney function indexes. To further estimate the predictive performance of the PTA model, it was compared with other prognostic models, including widespread clinical guidelines (BCLC, BCLC B sub-classification ^[9], HKLC, and the most recent Italian Liver Cancer [ITA.LI.CA] staging system ^[10]), other tumor-burden-based models (up-to-seven model ^[11], four-and-seven model ^[12], and six-and-twelve model ^[13]), and models incorporating other parameters (hepatoma arterialembolization prognostic [HAP] score, modified HAP [mHAP] II score ^[13], mHAP III score ^[14], albumin-bilirubin [ALBI] score ^[15], and the model to estimate survival in ambulatory HCC patients [MESIAH] ^[16]), by estimating the auROC and C-index.

Here, HCC patients could achieve two potential survival rates and predicted median survival times (MSTs) by choosing TACE or LR. The ideal LR candidate is defined as a patient whose MST could be extended by more than 50% compared with the MST of primary treatment if LR is adopted in the model. Similarly, ideal TACE candidates are those with an additional survival benefit of more than 50% compared to LR allocation in TACE prediction time. Considering that BCLC and HKLC ^[17] have clearly defined LR and TACE candidates, the ideal LR and TACE candidates of the PTA model were compared with candidates recommended by these two widely used guidelines.

5. Web implementation

After train and validation, the optimized PTA model was implemented as a web

interface, which generates the MST and depict integrated survival curves composed of LR and TACE according to the clinic parameters of specific patients provided by users. Relative algorithms of web development were described in the supplement 1.

6. Statistical analyses

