LR group (4.60 [3.00;7.00] cm) than in the TACE group (6.30 [4.00;9.90] cm); (b) The tumor lesions of HCC were relatively few in the LR group (1.0 [1.0-1.0] lesion) than in the TACE group (1.0 [1.0-2.0] lesions). In addition, the liver function of HCC patients (CPS and Child-Pugh stage) varied remarkably between the LR and TACE groups. A higher proportion of Child stage B patients were included in the TACE group (17.6%) than in the LR group (11.1%). The median follow-up was 54.0 months (IQR 38.7–69.2 months) for LR therapy and 36.1 months (IQR 24.7–54.7 months) for TACE. The 1-year, 3-year, and 5-year survival probability was 91.7%, 79.6%, and 70.8% for LR allocation, respectively, while 74.8%, 41.5%, and 26.4% for TACE treatment, respectively. Although there were significant differences between the LR and TACE groups, we perceived therapy type as a pivotal factor in the AI models to simulate a real-world clinical setting, considering the precise prediction of AI technologies.

Selection of the optimal AI model

We applied 10 kinds of machine learning survival algorithms in the train cohort, of which seven AI models performed well, with the C-index > 0.7 , and were retained: (i) random survival forest (RSF), (ii) conditional survival forest, (iii) DeepSurv algorithm, (iv) Extra Survival Trees, (v) Gompertz, (vi) standard Cox proportional hazards model (CoxPH), and (vii) PTA model based on the above six models. For model estimation, the C-index and IBS of these seven AI models were displayed in the Table 2. The C-index of the PTA model was 0.854 and 0.801 in the train and validation cohorts, respectively, which were higher than other six AI models except for the RSF model in train cohort. Even though the RSF model achieved the highest C-index (0.926) in the train set, while in the validation cohort, the C-index was only 0.765, indicating the potential presence of over-fitting in the RSF model. Given the C-index of the train and validation cohorts, the PTA model derived from the above six algorithms outperformed other single-algorithm models. As expected, the IBS of the six single algorithms and PTA algorithm was far smaller than 0.25, demonstrating their capability for clinical application (Supplement 2-3).

Predictive performance of the PTA model

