and TACE across different BCLC and HKLC stages and PS. Collectively, the K-M curves and HR consistently showed that the PTA algorithm could more effectively select TACE and LR candidates than the two authoritative therapeutic guidelines.

Web development and clinical application

To make an easy-to-apply tool and visualize the individual predictive results, we implemented the PTA models as a web interface, which could be freely accessed from www.pta4hcc.com. Users may input four groups of parameters: (a) demographic information, such as age and gender; (b) liver function; (c) tumor burden files; and (d) routine laboratory results like kidney function. The PTA model calculates the survival rate for each month when adopting different treatments (now including LR and TACE) and generates MST, all of which can be displayed on the user-friendly interface. For example, a 65-year-old man with hepatitis B virus infection and no prior treatment would possess a better prognosis if LR therapy was adopted instead of TACE after the diagnosis of HCC. His tumor burden characteristics are as follows: the number of tumors is four, the maximum tumor size is 8 cm, the AFP is 300 µg/L, and the ECOG or PS is 0. In addition, the information on the other two groups is also input into the website in the complete version. The output is his predicted survival curves derived from the PTA model, showing that LR's MST is 78 months, while TACE's MST is only 23 months (Supplement 10).

In parallel with the complete PTA algorithm, a concise version including the nine most important features was also developed on this website. This simple AI version could also calculate the integrated survival model immediately upon the input of these important features, especially for cases where some above-stated module features were unavailable. For example, a patient with two tumor lesions, a tumor size of 12 cm, 100 µg/L AFP, good PS, 120 g/L HGB, 35 U/L AST, 40 g/L ALB, and normal INR would benefit from TACE therapy rather than LR. The simulative survival curve indicates that the MST was 15 and 10 months for TACE and LR allocation, respectively (Supplement 11).

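### The predicted LR-versus-TACE difference, and the 458 and 2752 'erroneous allocation' counts built on it, cannot be separated from hospital and treatment-period effects, because no described input or analysis accounts for either

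*Combined protocol and SAP*

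**What the plan says.** - **Cohort (section 1, Study population):** 4991 patients were included after screening. The source is given as "Between January 2010 and October 2021, a total of 5816 consecutive HCC patients receiving LR or TACE from 15 Chinese tertiary hospitals". The train/validation split is random, and no stratifying factor is named.
- **Inputs (section 4, Model estimation):** the list of four modules ends with "c) demographic data, such as age and gender; and (d) routine laboratory indications, such as routine blood examination and kidney function indexes". Its second module covers tumor burden, and it opens with this statement: "The inputs of the PTA model mainly comprise four modules: (a) liver function, such as serum albumin, serum bilirubin, and coagulative function indexes".
- **Deployed tool (Web development and clinical application):** besides routine laboratory results, the input groups are described in these words: "Users may input four groups of parameters: (a) demographic information, such as age and gender; (b) liver function; (c) tumor burden files".
- **Treatment (Basic clinical characteristics):** after conceding significant differences between the groups, the text says "we perceived therapy type as a pivotal factor in the AI models to simulate a real-world clinical setting". Section 4 forms the contrast by changing the treatment for a given patient. A patient is an ideal candidate for a treatment if it lengthens predicted median survival time (MST) by more than 50%.
- **Use of the contrast (Comparison with clinical guidelines):** 458 LR patients are said to have needed TACE, and 2752 TACE patients (89.5%) are called erroneous allocations.
- **Adjustment:** section 6 (Statistical analyses) describes no stratification, random effect, matching or weighting by hospital or year. The subgroup analyses use BCLC stage, HKLC stage and performance status only.

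**The concern.** Switching the treatment factor while holding a patient's other inputs fixed estimates a treatment effect only if nothing outside those inputs is related to both treatment choice and survival. Hospital and treatment year are two obvious candidates in a cohort pooled over 15 centres and about 12 years. If centres that resect more also have different survival for other reasons, or if the treatment mix and background outcomes both changed over time, the model credits that difference to LR or TACE.

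Good prediction does not protect against this. The validation set is drawn at random from the same hospitals and years as the training set, so the validation C-index of 0.801 would look the same whether the treatment factor carried a treatment effect or a centre or period effect.

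At stake are statements that named numbers of patients received the wrong treatment, and a public web tool that displays two MSTs side by side.

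**Working it through.** **1. The plan's own counts.** 1916/4991 = 38.39% LR and 3075/4991 = 61.61% TACE, as stated. 1458 + 458 = 1916. 323 + 2752 = 3075, and 2752/3075 = 89.5%. So 2752 is every TACE patient whom the model did not pick as an ideal TACE candidate.

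**2. Where hospital or year could enter.**

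| Place | Hospital | Treatment year |
|---|---|---|
| Section 4, four input modules | not named | not named |
| Web tool, four input groups | not named | not named |
| Section 6, statistical analyses | not named | not named |
| Subgroup analyses (BCLC, HKLC, PS) | not named | not named |
| Train/validation split | random | random |

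**3. The pooled contrast.** From the stated 1-, 3- and 5-year survival, the crude LR/TACE hazard ratio is ln S(LR)/ln S(TACE):
- 1 year: ln 0.917/ln 0.748 = 0.30
- 3 years: ln 0.796/ln 0.415 = 0.26
- 5 years: ln 0.708/ln 0.264 = 0.26

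No hospital- or year-adjusted counterpart can be computed, because treatment counts and survival are not given by hospital or year.

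**4. Illustration of size (all hospital inputs assumed).** Take two hospital types, A and B, with LR shares of 70% and 20%. With 38.4% LR overall, 0.70w + 0.20(1 − w) = 0.384, so w = 0.368 of patients are in type A.
- Share of LR patients in A: 0.70 × 0.368/0.384 = 0.671
- Share of TACE patients in A: 0.30 × 0.368/0.616 = 0.179
- Spurious log hazard ratio: ln(r) × (0.671 − 0.179), where r is the mortality hazard ratio between types for reasons unrelated to treatment and not captured by the other inputs

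| r | Spurious factor | Share of ln 1.5 |
|---|---|---|
| 1.2 | 1.09 | 22% |
| 1.3 | 1.14 | 32% |
| 1.5 | 1.22 | 49% |

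LR shares of 60% and 25% give 1.07 to 1.15 for r from 1.2 to 1.5. If type A has the lower mortality, the factor favours LR; if the higher, it favours TACE. If the types do not differ in LR share, the factor is 1.

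More extreme inputs matter more. For a factor with hazard ratio g and prevalence pT in TACE and pL in LR, the bias is [1 + (g − 1)pT]/[1 + (g − 1)pL]. With g = 2 and 80% versus 20%, this is 1.8/1.2 = 1.50. With exponential survival, where the MST ratio is the inverse hazard ratio, that equals the 50% threshold with no true treatment difference at all.

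Smaller shifts matter near the cut-off. The concise web example (MST 15 versus 10 months) has a ratio of exactly 1.5; a factor of 1.09 moves it to 1.5/1.09 = 1.38 or 1.5 × 1.09 = 1.64.

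**5. Does the follow-up gap show a period imbalance?** The text reports: "The median follow-up was 54.0 months (IQR 38.7–69.2 months) for LR therapy and 36.1 months (IQR 24.7–54.7 months) for TACE". TACE survival at 36 months is 41.5%, so under half of TACE patients can have been observed beyond 36 months. The 36.1-month median is therefore not plain observed time in all TACE patients; it is reverse Kaplan–Meier or survivors only, and the documents do not say which. With identical treatment-date distributions in both groups, no loss to follow-up, and the stated survival figures (interpolated log-linearly, extrapolated beyond 5 years), survivors' median follow-up is:
- uniform accrual: 59.0 (LR) versus 31.5 (TACE) months, a gap of 27.5
- accrual weighted to recent years: 30.4 versus 18.6 months, a gap of 11.8

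The observed gap of 54.0 − 36.1 = 17.9 months lies between these. Mortality alone could produce it, so it does not establish that TACE patients were treated later.

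**The case against.** The strongest case against has four parts.

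- **The input list is open.** Section 4 introduces it with a word meaning 'for the most part' and gives examples only. Performance status, hepatitis B and prior treatment appear in the web example but in no listed module. Full model detail is deferred to Supplement 1 and a code repository, which are not in the text reviewed. This stands: absence is well supported by the web inputs, but not proved.
- **No confounding by hospital or year is shown.** A reader might infer from section 2 (for example "either a gelatin sponge or polyvinyl alcohol foam (PVA) particles were introduced to embolize tumor-feeding vessels either selectively or super-selectively") that technique differed by hospital and period. That section lists alternatives and ranges without attributing them to sites or years; they may follow tumor characteristics that are model inputs, and variation within TACE is not in itself confounding. A reader might also infer from the follow-up gap that TACE patients were treated later. The check above shows that this does not follow.
- **The illustration is assumed.** Its largest figure, 1.22, does not reach the 50% rule by itself and is about 15% of the crude log hazard ratio (ln 1.22/ln(1/0.26) = 0.148). This stands as a limit on size under those inputs, not as evidence that the effect is absent.
- **Adjustment would not repair everything.** Selection by tumor burden and liver function operates within hospitals too, and the 2752 count is a complement that includes TACE patients with small predicted differences. Both are true.

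None of this answers the core point: the plan makes patient-level allocation claims from a pooled contrast and describes no step that separates treatment from centre and period.

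**Conclusion.** The point holds in a limited form. No described input or analysis accounts for hospital or treatment year, so the LR-versus-TACE difference and the 458 and 2752 counts cannot be separated from centre and period effects. The stronger statement, that the difference does carry those effects, is not supported: it would require hospital or year to be related to both treatment and survival given the other inputs, and the documents show neither relation. Size and direction are unknown; the 1.09 to 1.22 range rests entirely on assumed LR shares and hazards and could favour either treatment. The conclusion also assumes that Supplement 1 and the code contain no such adjustment. If they do, the sponsor can close the point by saying so in the protocol.

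**What to change.** 1. Tabulate LR and TACE numbers by hospital and by treatment year.
2. Report the LR-versus-TACE contrast from a Cox model with the PTA inputs, stratified by hospital and adjusted for treatment year, next to the same contrast without hospital and year.
3. As a sensitivity analysis, refit PTA with treatment year and hospital as inputs, averaging over hospital for prediction, and recompute individual MSTs and candidate counts. The refit is needed because a stratified Cox contrast does not yield the ensemble's individual MSTs.
4. If the contrast or counts change materially, report the allocation-error counts as not separable from hospital and period.
5. State how median follow-up was calculated, and do not read treatment dates from it.

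The cost is modest reanalysis. Survival is timed from the first procedure, so treatment dates should exist, and hospital should be identifiable in a 15-centre dataset. Intervals will be slightly wider, and hospitals that performed only one procedure add nothing to the within-hospital contrast. Other confounding remains and needs separate treatment.

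### The candidate rule gives no uncertainty for an individual's predicted LR/TACE survival ratio, and the misallocation counts built on it leave no room for an undetermined group

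*Combined protocol and SAP*

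**What the plan says.** Section 4 (Model estimation) defines both kinds of candidate by a cut-off on predicted MSTs. The LR rule reads: "The ideal LR candidate is defined as a patient whose MST could be extended by more than 50% compared with the MST of primary treatment". For TACE: "Similarly, ideal TACE candidates are those with an additional survival benefit of more than 50% compared to LR allocation". Neither rule carries a standard error, an interval or a probability condition, and section 6 (Statistical analyses) adds none.

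Section 5 (Web implementation) says that the tool "generates the MST and depict integrated survival curves composed of LR and TACE according to the clinic parameters". The results section on web development gives two worked cases as single numbers: LR 78 against TACE 23 months, and, for the nine-feature version, "The simulative survival curve indicates that the MST was 15 and 10 months for TACE and LR allocation, respectively".

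Under 'Comparison with clinical guidelines' the labels become a verdict on past care. Of 1916 LR-treated patients, 1458 are called rightly allocated and 458 wrongly. Of 3075 TACE-treated patients, 323 are TACE candidates and 2752 (89.5%) are called erroneous.

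**The concern.** The label depends on a contrast between two predictions for the same patient, only one of which can ever be observed. The measures of performance in the text (C-index, AUC with its confidence intervals, calibration, integrated Brier score) describe groups. None says how far one patient's ratio would move if the model were refitted on another sample of the same size.

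There are reasons to expect that movement to matter. The text says of one of the six ensemble members that "in the validation cohort, the C-index was only 0.765, indicating the potential presence of over-fitting in the RSF model", and the ensemble's own C-index falls from 0.854 to 0.801. LR survival is still 70.8% at 5 years with a median LR follow-up of 54.0 months (upper quartile 69.2), so many LR medians probably rest on thin data or extrapolation. The displayed 78 months lies beyond that quartile.

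At stake are the candidate groups, their Kaplan–Meier comparisons, the statement that wrong allocation is common, and the firmness with which a public tool presents two MSTs.

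**Working it through.** **1. The plan's own figure.** 3075 − 323 = 2752, and 2752/3075 = 89.5%. The stated count reproduces, so the erroneous group is simply every TACE-treated patient who is not a TACE candidate. Taking TACE as the comparator in the LR rule, a TACE candidate has LR/TACE below 1/1.5 = 0.67 and an LR candidate has LR/TACE above 1.5. Anyone between 0.67 and 1.5 meets neither margin, yet a TACE-treated patient there is counted as an error. This holds even with perfect prediction. The text does not say how many of the 2752 lie in that band.

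**2. The LR arm.** 1458 + 458 = 1916, so again nobody is left undecided. But 1386 LR-treated patients are LR candidates, and 1916 − 1386 = 530, not 458. The gap of 72 (1458 − 1386) is not explained.

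**3. False labels from estimation error.** Suppose the true ratio is 1 and the estimated log ratio is normal with standard error SE. Then P(labelled ideal, either direction) = 2 × [1 − Φ(ln 1.5 / SE)], with ln 1.5 = 0.405. The documents do not give SE, so it is an assumption:

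| Assumed SE | P(false label) |
|---|---|
| 0.06 | about 0% |
| 0.17 | about 2% |
| 0.20 | 4.3% |
| 0.25 | 10.5% |
| 0.30 | 17.7% |
| 0.40 | 31.1% |

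The rate passes 5% at SE = 0.405/1.96 = 0.207.

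**4. What SE might be.** Inputs from 'Basic clinical characteristics': 1622 LR and 2570 TACE training patients; survival of 70.8% at 5 years (LR) and 41.5% at 3 years (TACE); median follow-up of 54.0 and 36.1 months. With constant hazards:
- LR: −ln(0.708)/60 = 0.00576 per month; deaths ≈ 1622 × (1 − e^(−0.00576 × 54)) ≈ 433.
- TACE: −ln(0.415)/36 = 0.0244 per month; deaths ≈ 2570 × (1 − e^(−0.0244 × 36.1)) ≈ 1506.

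With p standardised, independent inputs whose effects are fitted separately by arm, SE ≈ √[(1 + p)(1/433 + 1/1506)]. This gives 0.055 for p = 0 (treatment main effect only), 0.17 for p = 9, 0.25 for p = 20 and 0.30 for p = 30. A simulation of exponential regressions with a true ratio of 1 for every patient (60 replicates per p) gave false-label rates of 2.0%, 10.3% and 17.4% for p = 9, 20 and 30, against 1.9%, 10.5% and 18.2% from the formula. The text does not give the number of inputs in the complete model.

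**5. The worked cases.** 15/10 = 1.50 exactly, which does not exceed 50%, though the text says the patient would benefit from TACE. Its 95% interval would be 1.5 × e^(±1.96 × 0.25) = 0.92 to 2.45 at SE 0.25, and 1.07 to 2.10 at SE 0.172 (nine inputs). 78/23 = 3.39, with an interval of 2.08 to 5.54 at SE 0.25.

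**The case against.** The strongest reply is that the 50% margin is itself a buffer. It holds false labels below 5% for any SE under about 0.21, and nothing in the text shows that SE is larger. This stands, and for that reason the size is given only as a range.

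Several stronger readings are tempting, and the documents do not support them:

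- *SE 0.25 is a minimum.* It is not. Shrinkage, fewer inputs or effects shared across arms all lower it. Treatment as a main effect alone gives about 0.055 and essentially no false labels. The ensemble as a whole cannot be of that kind, because its labels go in both directions, but this does not fix its SE.
- *The ratio is far less precise than either prediction.* At p = 20 the LR prediction alone has SE √(21/433) = 0.220, against 0.250 for the ratio, about 14% more. In a pooled model shared error cancels, and the ratio may be the more precise.
- *The labels are mostly noise.* 1386/1916 = 72.3% of LR-treated patients are LR candidates. Symmetric error around no difference cannot put more than 50% on one side. The 10.5% TACE share would match SE of about 0.32, but a match is not evidence. Non-random treatment choice is the likelier source of one-sided labels; the text itself reports significant differences between the groups.
- *The 78 against 23 months case is noise.* At SE 0.25 its interval stays above 1.5.
- *Every result is affected.* As described, C-index, AUC, calibration and Brier score do not use the label.
- *Users are shown no uncertainty.* This cannot be confirmed. The text says "Relative algorithms of web development were described in the supplement 1", the displays are in Supplements 10 and 11, and the code is external. None of these was available.

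**Conclusion.** The point holds in a limited form. Two parts need no assumption: the described rule uses point predictions with no stated individual uncertainty, and the TACE count treats every non-candidate as an error, including any patient between the two margins. The part that depends on assumptions is how often estimation error alone produces an ideal label: about 0% to 31% at a true ratio of 1 for SEs of 0.06 to 0.40, and about 10% at 0.25. Those figures rest on a normal log ratio and, for the SE, on a simple parametric model rather than the six-member ensemble. The unmeasured rate is the finding; no particular rate is shown. It should be settled before the 458 and 2752 counts are quoted as misallocations. It does not by itself overturn the prognostic performance results.

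**What to change.** - Refit the PTA pipeline on about 200 bootstrap samples of the training set and store each patient's MST ratio. Hyperparameters may be held fixed to save time; if so, say so, since this can understate the variation.
- Report an interval for each patient's ratio, at a level fixed beforehand, for example 90%.
- Keep the 50% margin as the point rule. In the analysis, report as undetermined, not as erroneous, every patient who meets neither the LR nor the TACE margin or whose interval includes 1. Restate the 458 and 2752 counts on that basis, account for the gap of 72 in the LR arm, and state the comparator in the LR rule.
- On the web page, show the interval beside each MST and ratio, and flag any MST beyond observed follow-up.
- State that the interval covers sampling error only. Bootstrap does not address confounding from non-random treatment choice, and a narrow interval should not be read as if it did.

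The interval condition does little if SE is moderate. At SE 0.25 a 90% interval excludes 1 only when the ratio exceeds e^(1.645 × 0.25) = 1.51, hardly more than 1.50. At SE 0.40 the cut-off becomes 1.93 and false labels fall from 31% to about 10%. The undetermined group is worth having at any SE, because it removes the forced split.

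The cost is computing time for repeated fits of a six-model ensemble, work to serve intervals to new web users, and fewer patients carrying a label.
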